7.3 Safety/Tolerability

Analyses will be performed for all patients having received at least one dose of study drug. The study will use the CTCAE version 4.03 for reporting of non-hematologic adverse events (<http://ctep.cancer.gov/reporting/ctc.html>) and modified criteria for hematologic adverse events.

8.0 ADVERSE EVENTS

8.1 Adverse Event Reporting Requirements

Adverse event (AE) monitoring and reporting is a routine part of every clinical trial and is done to ensure the safety of subjects enrolled in the studies as well as those who will enroll in future studies using similar agents. Data on adverse events will be collected from the time of the initial study treatment administration through 30 days after the last [dose of study treatment. Any serious adverse event that occurs more than [30] days after the last study treatment and is considered related to the study treatment must also be reported. Serious Adverse Events (SAEs) will continue to be followed until:

- Resolution or the symptoms or signs that constitute the serious adverse event return to baseline;
- There is satisfactory explanation other than the study treatment for the changes observed; or
- Death.

The investigator is responsible for the detection, documentation, grading and assignment of attribution of events meeting the criteria and definition of an AE or SAE. The definitions of AEs and SAEs are given below. It is the responsibility of the principal investigator to ensure that all staff involved in the trial is familiar with the content of this section.

Any medical condition or laboratory abnormality with an onset date before initial study treatment administration is considered to be pre-existing in nature. Any known pre-existing conditions that are ongoing at time of study entry should be considered medical history.

All events meeting the criteria and definition of an AE or SAE, as defined in Section 8.3, occurring from the initial study treatment through 30 days following the last dose of the study treatment must be recorded as an adverse event in the patient's source documents and on the CRF regardless of frequency, severity (grade) or assessed relationship to the study treatment.

In addition to new events, any increase in the frequency or severity (i.e., toxicity grade) of a pre-existing condition that occurs after the patient begins study treatment is also considered an adverse event.

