2.4 Endpoints

Primary Endpoint

1. Proportion of subjects who receive 4 doses of pembrolizumab and at least one session of treatment of SBRT within 15 weeks from the first dose of pembrolizumab.

Secondary Endpoints

1. Frequency and severity of Grade 3-5 drug-related adverse events graded by CTCAE v4.30.
2. Overall response proportion (Best Overall Response) and Progression Free Survival by RECIST, and Immune Related Response Criteria.

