5.2 Toxicities and Dosing Delays/Dose Modifications

Any patient who receives one dose of pembrolizumab will be evaluable for toxicity. Each patient will be assessed for the development of toxicity according to the Time and Events Table (Section 6.4). Toxicity will be assessed according to the NCI Common Terminology Criteria for Adverse Events (CTCAE), version 4.03. Dose adjustments should be made according to the system showing the greatest degree of toxicity.

Dose modifications in strength are not permitted for pembrolizumab

Dosing delays for Pembrolizumab:

- No dose delays for pembrolizumab are needed for hematologic changes.

- With any grade 2 or higher **non-hematologic toxicity deemed to be related to pembrolizumab**, hold pembrolizumab and refer to section 5.2.1. If adverse event is not an event of interest and improves to grade 1 or better, pembrolizumab may be resumed.
- If non-hematologic toxicity does not improve to grade 1 or better in 12 weeks from prior dose, discontinue pembrolizumab.

5.2.1 **Events of interest for Pembrolizumab:**

Certain adverse events that are possibly immune mediated warrant special monitoring and management, and are outline below to guide investigators.

5.2.1.1 **Pulmonary:**

Rule out non-inflammatory causes. If non-inflammatory cause, treat accordingly and continue protocol therapy. Evaluate with imaging and pulmonary consultation.

Grade of pneumonitis (NCI CTCAE v4.03)	Management	Follow-up
Grade 1 Radiographic Changes Only	
 • Consider delay of pembrolizumab • Monitor for symptoms every 2-3 days • Consider pulmonary and infectious disease consultations 	
 • Re-image at least every 3 weeks • If worsening, treat as grade 2, 3 or 4
Grade 2 Mild to moderate new symptoms	
 • Delay pembrolizumab • Consult pulmonary and infectious disease • Monitor symptoms daily, consider hospitalization • 1.0mg/kg/day methylprednisolone IV or oral equivalent • Consider bronchoscopy and/or lung biopsy 	
 • Re-image every 1-3 days • Consider prophylactic antibiotics while on steroids • If improves: 
 • When symptoms return to near baseline, taper steroids over at least one month • When steroids are at 10mg oral prednisone (or equivalent) or below, resume pembrolizumab • If not improving after 2 weeks or worsening, treat as grade 3 or 4

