Grade 3 or 4 Severe new symptoms and/or new or worsening hypoxia	
 • Discontinue pembrolizumab • Hospitalize • Consult pulmonary and infectious disease • 1-2mg/kg/day methylprednisolone IV or IV equivalent • Add prophylactic antibiotics for opportunistic infections like PCP • Consider bronchoscopy and/or lung biopsy 	
 • If improves to baseline: 
 • Taper steroids for at least 6 weeks • If not improving after 48 hours or worsening 
 • Add additional immunosuppressive agent(s) (e.g. infliximab, cyclophosphamide, intravenous immunoglobulin or

5.2.1.2 Gastrointestinal:

Rule out non-inflammatory causes. If non-inflammatory cause, treat accordingly and continue protocol therapy. Opiates or narcotics may mask symptoms of perforation. Infliximab should not be used in case of perforation or sepsis.

Grade of diarrhea/colitis (NCI CTCAE v4.03)	Management	Follow-up
Grade 1 
 Diarrhea of less than 4 stools per day over baseline or asymptomatic colitis 	
 Continue pembrolizumab Symptomatic treatment such as loperamide 	
 Close monitoring for worsening symptoms Educate patient to report worsening immediately If worsening, treat as grade 2,3 or 4
Grade 2 
 Diarrhea of 4-6 stools per day over baseline OR IV fluids needed < 24 hours due to diarrhea OR Colitis with abdominal pain or blood in stool 	
 Delay pembrolizumab Administer corticosteroids (initial dose of 1 to 2 mg/kg/day prednisone or equivalent followed by a taper) Consider prophylactic antibiotics for opportunistic infections like PCP if steroid treatment prolonged 	
 If improves to grade 1, resume pembrolizumab Resume pembrolizumab if the event improves to grade 0 or 1 within 12 weeks and corticosteroids have been reduced to the equivalent of ≤ 10mg oral prednisone per day When symptoms improve to grade 1, taper steroids over at least one month If worsening, treat as grade 3 or 4

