Grade 3 
 Diarrhea ≥ 7 stools per day over baseline OR IV fluids needed for ≥ 24 hours due to diarrhea OR Colitis with severe abdominal pain or medical intervention indicated 	
 Delay pembrolizumab 1-2mg/kg/day methylprednisolone IV or IV equivalent Start prophylactic antibiotics for opportunistic infections such as PCP Consider lower endoscopy 	
 If improves 
 Continue steroids until symptoms are grade 1, then taper over at least one month Resume pembrolizumab if the event improves to grade 0 or 1 within 12 weeks and corticosteroids have been reduced to the equivalent of ≤ 10mg oral prednisone per day If persists for >3-5 days or recurs after improvement, add infliximab 5mg/kg if no contraindication (Note: infliximab should not be used in cases of perforation or sepsis)
Grade 4 Life threatening or perforation	
 Discontinue pembrolizumab 1-2mg/kg/day methylprednisolone IV or IV equivalent Start prophylactic antibiotics for opportunistic infections such as PCP Consider lower endoscopy 	
 If improves 
 Continue steroids until symptoms are grade 1, then taper over at least one month If persists for >3-5 days or recurs after improvement, add infliximab 5mg/kg if no contraindication (Note: infliximab should not be used in cases of perforation or sepsis)

5.2.1.3 Endocrinopathy:

Rule out non-inflammatory causes. If non-inflammatory cause, treat accordingly and continue protocol therapy. Consider visual field testing, endocrinology consultation and imaging.

Endocrinopathy	Management	Follow-up
Asymptomatic thyroid-stimulating hormone (TSH) elevation	
 Continue pembrolizumab If TSH <0.5 x LLN or TSH >2x ULN, or consistently out of range in subsequent measurements, include free T4 in subsequent measurements as clinically indicated Consider endocrinology consult 	
Symptomatic Hypothyroidism	
 Initiate thyroid replacement 	
Symptomatic Hyperthyroidism	
 Delay pembrolizumab Consider endocrinology consult Initiate anti-thyroid drug 	
 Resume pembrolizumab when symptoms of hyperthyroidism are controlled and thyroid function is improving

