
Grade 3 or 4
 
 Severe symptoms Limiting self-care ADLs 	
 Discontinue pembrolizumab Consult Neurology Treat symptoms per institutional guidelines 1-2mg/kg per day IV methylprednisolone or IV equivalent Add prophylactic antibiotics for opportunistic infections 	
 If improves to grade 2, taper steroids over at least one month If worsens, consider IVIG or other immunosuppressive therapies per institutional guidelines

Meningitis or Encephalitis
	
 Discontinue pembrolizumab 1-2mg/kg per day IV methylprednisolone or IV equivalent Add prophylactic antibiotics for opportunistic infections 	
 If improves, convert to oral steroids (prednisone 60mg/day or equivalent) When symptoms improve to \leq grade 1, taper steroids over at least one month

5.2.1.6 Skin:

Rule out non-inflammatory causes. If non-inflammatory cause, treat accordingly and continue protocol therapy

Grade of Rash (NCI CTCAE v4.03)	Management	Follow-up

Grade 1-2 Covering \leq 30% body surface area (BSA)
	
 Symptomatic therapy (such as antihistamines, topical steroids) Continue pembrolizumab 	
 If persists 1-2 weeks or recurs 
 Consider skin biopsy Delay pembrolizumab Consider 0.5-1mg/kg/day methylprednisolone IV or oral equivalent Once improving, taper steroids for at least one month Consider prophylactic antibiotics for opportunistic infections like PCP Resume pembrolizumab if rash improves to \leq grade 1 within 12 weeks and corticosteroids have been reduced to \leq 10 mg oral prednisone or equivalent per day If worsens, treat as grade 3 or 4

Grade 3-4 Covering $>$30% BSA or life threatening consequences
	
 Delay or discontinue pembrolizumab Consider skin biopsy If patient is diagnosed with Stevens-Johnson Syndrome (SJS) or Toxic Epidermal Necrolysis (TEN), pembrolizumab must be discontinued Consult dermatology 	
 If improves to grade 1: 
 Taper steroids over at least one month Resume pembrolizumab if rash improves to \leq grade 1 within 12 weeks and corticosteroids have been reduced to \leq 10 mg oral prednisone or equivalent per day

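### Recording of non-serious adverse events stops 30 days after the last study treatment, while a toxicity hold may last 12 weeks, so a late related grade 3 event in a patient who never resumes need not reach secondary endpoint 1

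*Combined protocol and SAP*

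**What the plan says.** Section 8.1 states that events "occurring from the initial study treatment through 30 days following the last dose of the study treatment must be recorded as an adverse event", whatever their grade, seriousness or attribution. After that one duty remains: "Any serious adverse event that occurs more than [30] days after the last study treatment and is considered related to the study treatment" must still be reported. The clause on worsening covers "any increase in the frequency or severity (i.e., toxicity grade) of a pre-existing condition", and 8.1 treats a condition as pre-existing only if it began before the first study treatment. Following an event to resolution is required for serious events only.

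Section 5.2 sets the limit on a hold: "If non-hematologic toxicity does not improve to grade 1 or better in 12 weeks from prior dose, discontinue pembrolizumab". Several tables in 5.2.1 keep resumption open that long. For diarrhea/colitis, the grade 2 row says "If worsening, treat as grade 3 or 4", and the grade 3 row still says "Resume pembrolizumab if the event improves to grade 0 or 1 within 12 weeks". For grade 3-4 rash the instruction is "Delay or discontinue pembrolizumab", again with a 12-week limit for resuming.

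Secondary endpoint 1 (section 2.4) is "Frequency and severity of Grade 3-5 drug-related adverse events graded by CTCAE v4.30". It names neither a time window nor a seriousness condition. Section 11.2 treats it descriptively. The Time and Events Table (6.2) marks a toxicity evaluation at End of Treatment and none in follow-up, and it does not date the End of Treatment visit relative to the last dose.

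**The concern.** The collection window is tied to the last treatment actually given, while the period in which a held patient remains on protocol is tied to the hold rule. In a 21-day schedule the window closes 30 - 21 = 9 days after the first withheld dose falls due, although the hold may continue for weeks.

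Whether an event during the hold must be recorded therefore depends on what happens next. If the patient recovers and resumes, the last dose moves forward and the event falls inside the window. If the patient does not recover, the last dose stays where it was and the event falls outside. Any loss is among patients who tolerated treatment least well, and it can only lower the reported grade 3-5 frequency. Safety of the combination is secondary objective 1, so the rule for counting these events should not depend on resumption.

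**Working it through.** The plan gives no figure on this point, so there is none to reproduce. Days count from the last pembrolizumab dose (day 0).

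**Inputs.** Recording window: 30 days after last study treatment (8.1). Maximum hold: 12 weeks = 84 days from the prior dose (5.2). SBRT: after day 1 of cycle 1, starting no later than the start of cycle 2 (5.1). N = 20 (11.1).

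**Length of the gap within a hold.** With L the day of the last study treatment, uncovered days = 84 - (L + 30).

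- Pembrolizumab last, L = 0: 84 - 30 = 54 days (days 31 to 84).
- Hold after dose 1, SBRT ending day 10 to 28 (assumed): window closes day 40 to 58, leaving 44 to 26 days.
- Hold after dose 2, SBRT ending 3 to 14 days after that dose (assumed): window closes day 33 to 44, leaving 51 to 40 days.

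**Same event, two outcomes.** Take a non-serious, related grade 3 event starting on day 31, with L = 0. A patient who resumes on day 84 has a window running to at least 84 + 30 = day 114, so the event must be recorded. A patient who never resumes has a window that closed on day 30, so it need not be.

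**Where 5.2 leaves the path open.**

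- Diarrhea/colitis: held at grade 2; the grade 3 row still allows resumption within 12 weeks.
- Rash: held if grade 1-2 persists or recurs; resumption within 12 weeks in both rows.
- Pancreatic: held for grade 2-3 pancreatitis or grade 3 enzymes, with a 12-week limit.
- Renal: the grade 2-3 row and the grade 4 row both allow resumption within 12 weeks.
- Grade 2 pneumonitis: without improvement after 2 weeks it is managed as grade 3-4, that is, discontinued (day 21 + 14 = day 35 if the hold began on day 21). If it improves, steroids are tapered over at least a month before resumption, so a long hold does arise.
- Toxicities not listed in 5.2.1: the general 12-week rule applies.
- Hepatic, by contrast, largely closes the path: grade 2 persisting beyond 5-7 days is managed by discontinuation (day 26 to 28 on the same start).

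**Effect on the endpoint.** One patient is 1/20 = 5 points. Exact (Clopper-Pearson) 95% intervals: 0/20 gives 0% to 16.8%; 1/20 gives 0.1% to 24.9%.

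**How many patients.** The documents give no rates. As an illustration only, assume 5% to 20% of patients are held and never resume, and 5% to 25% of those have such an event. Expected missed patients = 20 × 0.05 × 0.05 = 0.05 up to 20 × 0.20 × 0.25 = 1.0. The chance of at least one is 1 - (1 - 0.0025)^20 = 5% up to 1 - (1 - 0.05)^20 = 64%. The chance that no patient is held without resuming is 0.95^20 = 36% at the low rate and 0.80^20 = 1% at the high rate.

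**The case against.** Sections 2.4 and 8.1 can be read together: the endpoint is described from whatever 8.1 collects, and silence on time in 2.4 does not promise unlimited follow-up. That is fair, and the two sections do not contradict each other outright. What remains is that the window, so read, treats the same event differently according to resumption, which no section states as intended.

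A reader might infer that an event which began on treatment and worsens to grade 3 after day 30 is excluded. The documents do not support that. The event was already recordable, the investigator is responsible for grading, and 5.2 requires the grade to be followed to decide on resumption. Section 8.1 is silent on upgrading a non-serious event after the window; it does not clearly exclude it. The firm part of the point is the event that starts after day 30.

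Other safeguards reduce the loss. Many grade 3 events of these kinds will be serious, through hospitalization or as important medical events under 8.2, and so remain reportable if related. Section 5.7 requires the reason for stopping to be documented in the source, and there is a toxicity evaluation at End of Treatment. During an open hold staff cannot know that the prior dose was the last and will probably keep recording. All of this stands, but none of it obliges entry of a late non-serious event on the case report form.

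**Conclusion.** The point holds and is minor. By the stated rule, a non-serious, related grade 3 event starting in a hold after the 30-day window need not be recorded for a patient who never resumes, yet must be for one who does. The uncovered stretch within a hold is up to 54 days when pembrolizumab was the last study treatment, and 26 to 51 days under the SBRT timings assumed above.

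Two stronger inferences should be resisted. One is that the grade 3-5 rate will be materially understated: the affected group is small and may be empty, the count cannot be derived, and one missed patient is within sampling error at N=20. The other is that 54 days bounds all late events. It is a maximum only within an open hold; the 30-day cutoff for non-serious events applies to every patient off treatment, which is an ordinary convention.

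The safety analysis is descriptive, and the primary feasibility conclusion is unaffected.

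**What to change.** In 8.1, for all patients, require recording of grade 3-5 events at least possibly related to study treatment, serious or not and including worsening of an earlier event to grade 3 or higher. The period should run through the later of (a) 30 days after the last study treatment and (b) 30 days after the permanent discontinuation date already documented under 5.7. Include anything found at the existing End of Treatment toxicity evaluation.

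Because discontinuation cannot precede the end of the hold, this covers the whole hold: stopping on day 35 gives day 65, and stopping on day 84 gives day 114. One rule for everyone matters, because extending the window only for patients held for toxicity would itself make ascertainment unequal.

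In 11.2, report events within 30 days of the last study treatment and later events separately, flagging those after new anti-cancer therapy. This preserves the conventional 30-day figure.

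The cost is a sentence in each section, a row in the adverse event table and slight extra data entry. No visits are added, so detection after End of Treatment stays unsystematic. Attribution of late events is weaker, hence the flag, and the reported rate may be slightly less favourable.

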8.2 Definitions

Adverse Event

An adverse event (AE) is any untoward medical occurrence in a patient receiving study treatment and which does not necessarily have a causal relationship with this treatment. An AE can be any unfavorable and unintended sign (including an abnormal laboratory finding), symptom, or disease temporally associated with the use of an experimental intervention, whether or not related to the intervention.

- *Diagnostic and therapeutic non-invasive and invasive (i.e., surgical) procedures will not be reported as adverse events. However, the medical condition for which the procedure was performed must be reported if it meets the definition of an adverse event unless it is a pre-existing (prior to protocol treatment) condition.*
- *Abnormal laboratory values or test results constitute adverse events if they induce clinical signs or symptoms or require therapy. They are to be captured under the signs, symptoms or diagnoses associated with them.*

Serious Adverse Event

An adverse event is considered “serious” if, in the view of either the investigator it results in any of the following outcomes:

- Death
If death results from (progression of) the disease, the disease should be reported as event (SAE) itself.
- A life-threatening adverse event
An adverse event is considered ‘life-threatening’ if, in the view of either the investigator [or sponsor], its occurrence places the patient or subject at immediate risk of death. It does not include an adverse event that, had it occurred in a more severe form, might have caused death.
- Inpatient hospitalization or prolongation of existing hospitalization for ≥ 24 hours.
- A persistent or significant incapacity or substantial disruption of the ability to conduct normal life functions
- A congenital anomaly/birth defect
- Important medical event
Any event that may not result in death, be life-threatening, or require hospitalization may be considered serious when, based upon appropriate medical judgment, they may jeopardize the patient and may require medical or surgical intervention to prevent one of the outcomes listed in this definition of “Serious Adverse Event”. Examples of such medical events include allergic bronchospasm requiring intensive treatment in an emergency room or at home; convulsions that do not result in inpatient hospitalization or the development of drug dependency or drug abuse.

Previously planned (prior to signing the informed consent form) surgeries should not be reported as SAEs unless the underlying medical condition has worsened during the

course of the study. Preplanned hospitalizations or procedures for preexisting conditions that are already recorded in the patient's medical history at the time of study enrollment should not be considered SAEs. Hospitalization or prolongation of hospitalization without a precipitating clinical AE (for example, for the administration of study therapy or other protocol-required procedure) should not be considered SAEs. However, if the preexisting condition worsened during the course of the study, it should be reported as an SAE.

Expected Adverse Events

An adverse event (AE) is considered "expected" if:

- For approved and marketed drugs or devices, those adverse events are described in the approved Package Insert (Label).
- For investigational new drugs or devices, those adverse events are described in the FDA Investigator's Brochure.
- In clinical research studies, information on expected adverse events is also summarized in the protocol and in the consent document. See section 9.1 for the list of expected adverse events related to the drug under study.

Unexpected Adverse Event

An adverse event (AE) is considered "unexpected" if it is not described in the Package Insert, Investigator's Brochure, in published medical literature, in the protocol, or in the informed consent document.

